1.0 PROTOCOL SUMMARY AND/OR SCHEMA

The objective of this study, entitled "Pilot Trial of the Robotic Uterine Manipulator," is to evaluate the feasibility, safety and utility of a newly developed robotic uterine manipulator system. The [name] Automated Uterine Manipulator (BAUM) was developed by [name] in collaboration with the MSK Innovation and Technology Team (ITT) and with the support of the Device Design and Development Fund (3DF). Subsequent funding for the external development by a development engineering partner with an extensive track record in developing medical devices, MPR Inc., has been provided through [name] discretionary funding and institutional donor funding. There will be a single robotic unit available for testing that robotically positions the clinically established and FDA approved V-Care uterine manipulator. Our hypothesis is that use of the BAUM will be feasible in nearly all patients undergoing total laparoscopic or robotic-assisted hysterectomy, will provide sufficient uterine manipulation and will have a low rate of associated intraoperative complications.

All patients undergoing total laparoscopic or robotic-assisted hysterectomy that will include the use of a uterine manipulator would be eligible for participation in this study. Annually, MSK's Gynecology Service performs approximately 500 laparoscopic and robotic-assisted hysterectomies. It is estimated that 90% of these patients would be eligible for this study. The standard protocol accrual rate is 30-35%. We estimate that this pilot study will reach the target accrual of 40 patients in one year or less.

Eligible patients will be consented for the study at the time of their surgical consultation. At the time of surgery, the BAUM prototype will be available for placement, use, and evaluation. The robotic manipulator will be affixed to the V-Care at the start of each case. The V-Care is an FDA approved uterine manipulator which will attach to the investigational BAUM. The V-Care manipulator will be used internally to move or manipulate the uterus to ensure that the surgeon's view is not blocked, so that he or she can perform the surgery effectively and safely, given the nearness of surrounding organs, such as the ureters, bladder, and colon. Historically a clinical staff member was responsible for positioning the instrument according to verbal commands from the surgeon. The BAUM will be utilized in place of a clinical staff member, attaching directly to the V-Care.

Unsuccessful mounting will be documented on the product evaluation form and the V-Care uterine manipulator of the surgeon's choice will be used manually instead. Successful docking of the robotic manipulator to the V-Care will be documented on the product evaluation form by the attending surgeon. If there are associated intraoperative complications, such as uterine perforation or cervical laceration, continued use of the robotic manipulator will be at the discretion of the attending surgeon. Product evaluation forms are required to be completed by the attending surgeon by the end of the case. Forms will be collected in the OR or immediately following surgery. Surgical videos and/or photos will be obtained for analysis of the robotic manipulator.

The goal is to have at least 8 of the 12 surgeons on the Gynecology Service use and evaluate the robotic manipulator. All responses on the product evaluation form will be

analyzed to determine utility of the device. Safety will be measured by the number of robotic uterine-manipulator-associated intraoperative complications. Patients will be followed by the study team for 25-35 days after surgery.

2.0 OBJECTIVES AND SCIENTIFIC AIMS

- Primary Objective: To determine the feasibility and safety of the robotic manipulator in
 women undergoing total laparoscopic or robotic-assisted hysterectomy at MSK. Feasibility
 will be determined by whether successful manipulation of the V-Care manipulator is
 achieved. Safety will be measured by the number of intraoperative complications
 attributed to the robotic manipulator.
- Secondary Objective: To determine the utility of the robotic manipulator in patients
 undergoing total laparoscopic or robotic-assisted hysterectomy at MSK. Utility will be
 measured by the product evaluation form provided by the Department of Perioperative
 Services.

3.0 BACKGROUND AND RATIONALE

Hysterectomy for benign and malignant disease is one of the most common surgical procedures among women in the United States; approximately 600,000 of these procedures are performed annually. Traditionally, hysterectomies have been performed using the open approach via laparotomy. However, since the introduction of laparoscopic and robotic-assisted gynecologic surgery, minimally invasive hysterectomy has become the preferred surgical method with studies showing that greater than 70% of cases are performed using these techniques. At MSKCC we do approximately 500 minimally invasive hysterectomies each year. This surgical method is especially well-suited for the treatment of endometrial cancer, as laparoscopic and robotic-assisted hysterectomy are associated with fewer postoperative adverse events and shorter hospital stay without compromised oncologic outcomes. These recent surgical options are particularly beneficial to the morbidly obese endometrial cancer population, affording these patients complete surgical staging without the need for a large laparotomy incision.

Uterine manipulation is paramount to performing a successful, uncomplicated laparoscopic or robotic-assisted hysterectomy. The ability to deviate the uterus in any desired direction is essential for visualization, dissection, and safety, especially given the proximity of the ureters, bladder, and colon.

Manual manipulations of uterine positioning instruments are inefficient as they require a clinical staff member to stand and position the manipulator according to verbal commands from the surgeon. Communicating the intended anatomical location and having the assistant reliably follow these instructions is challenging as real world anatomical positional instructions are often not easy to verbalize. Furthermore, requiring a person to

hold the anatomy under positive pressure for long periods of time intraoperatively can result in anatomical drift, as well as fatigue and injury to the assisting staff member.

The BAUM system (Figure: 1) has been designed to fit easily in the space required for positive uterine positioning regardless of the minimally invasive surgery method, whether robotic assisted or laparoscopic. The system uses a proven robotic arm unit specifically sourced for its utility and form factor. A custom interface that allows the BAUM to positively attach to the V-Care has been designed and implemented. The surgical control panel (Figure: 2) from which the surgeon will control the movements of the BAUM arm, will sit alongside the Da Vinci surgeon console for robotic cases or be sterilely draped and placed near the operating surgeon. The arrows on the figure indication that the arm can move in all directions including, up, down, left, right, rotation to the left and rotation to the right.

We hypothesize that the robotic manipulator will be easy to dock to the V-Care and will not require any special setup outside of the established patient setup.

[figure not shown]

Figure: 1

Figure: 2

MSK is poised to be a leader in innovation and technology development, presenting a unique opportunity for the Department of Surgery to become more involved in planning, operationalizing, and commercializing technological advances. The ITT program seeks to increase recognition of surgeon-driven ideas, increase intellectual property protection and increase support for the development of new and evolving technologies. Within this framework, the ITT program has distributed and funded requests for applications aimed at encouraging surgeon-inventors to put ideas forward. The first of these is the Device Design and Development Fund (3DF). The development and creation of several prototypes of the robotic uterine manipulator has been funded by the 3DF grant. Analysis of the device on a clinical trial is the next step in development; tests of its utility and safety will spur design improvements and modifications prior to production. The robotic manipulator could replace existing uterine manipulators in use at MSK. Ultimately, the device has the potential to decrease OR time, decrease OR costs, and increase patient safety.

4.0 OVERVIEW OF STUDY DESIGN/INTERVENTION

4.1 Design

This feasibility study will aim to accrue 40 patients in one year or less. All patients who are consented for a total laparoscopic or robotic-assisted hysterectomy will be eligible for the trial, unless the surgeon does not plan to use a uterine manipulator. On average, the GYN Disease Management Team performs about 500 robotic and laparoscopic hysterectomies per year.

[name] and [name] will provide an educational training session to all GYN surgeons and fellows at an attending's meeting and/or a GYN Treatment Planning Conference prior

to protocol activation. All surgeons that will use the device will be provided with this training.

[name] will receive composite results to provide consulting guidance regarding the device and any further manufacturing. There will not be any PHI included in the information provided to him.

Contingent on successful completion of this trial, an application for FDA approval may be filed for this device.

4.2 Intervention

The robotic manipulator will be placed at the start of each case. The manipulator will be cleaned and sanitized using the same process as other reusable OR devices. Feasibility will be determined by the rate of successful robotic manipulator docking and if the manipulation of the uterus was successful for the duration of the procedure. Placement of a BAUM will be noted on the operative note. In addition, we have included a question on the product evaluation form (Appendix A). Safety will be measured by the number of intraoperative complications reported during surgery. Of 554 minimally invasive hysterectomies performed from July 2014 through Jun 2015, only 2 intraoperative complications were reported. Patients would also be assessed for complications immediately after surgery. Utility and ease of use will be assessed by the product evaluation form provided by the Department of Perioperative Services. The form will be completed by all GYN Surgeons who use the robotic manipulator. The goal is to have at least 8 of the 12 surgeons use the robotic manipulator and evaluate the product. A surgeon will have to complete one docking with the BAUM and one clinical manipulation of the uterus to participate. The responses from all surgeons and cases will be analyzed to determine the utility of the manipulator. Surgical videos and/or photos will be obtained for analysis of the robotic manipulator. After surgery, patients will be followed by the study team for 25-35 days to record any postoperative complications that may be related to the robotic device. If the standard-of-care post-operative visit is outside of the 25-35 day window, a clinician will call the patient during the 25-35 day window and document any post-operative complications. The complications will be tracked in the study database. There are no anticipated additional risks above what can be experienced during the scheduled surgery performed without the BAUM. If a complication occurs, [name] and/or the treating physician will review to determine if it is attributable to the use of the BAUM. Attribution determination will be made based on the type of complication and whether it is a medical or anesthetic complication of surgery, for example surgery complications may include bleeding or infection. Participants will be monitored for all complications for 25-35 days post surgery.

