7.0 ASSESSMENT/EVALUATION PLAN

After obtaining informed consent, data regarding the patient's treatment and disease status will be abstracted from the medical record for the purpose of characterizing the sample. Data will be collected regarding the disease stage, surgical characteristics, and patient demographics.

During the surgery, the surgeon will note any intraoperative complications. These are recorded on the operative report. The operative report is synoptic. Nomenclature and severity of grading for intraoperative complications is standardized. The surgeon or fellow will also note the feasibility of docking the V-Care uterine manipulator. If the robot cannot be docked with the V-Care and does not stay securely in place, the reason will be recorded.

After surgery, the surgeon will complete the product evaluation form and deliver it to the RSA. The evaluation form asks questions to determine ease of use, specifically, whether manipulation with the BAUM was successful, whether the device was successfully docked, the occurrence of any complications, and how easy it was to use. Patients will be followed by the study team for 25-35 days after surgery to track any postoperative complications

related to the robotic device. The complications will be tracked in the study database. There are no anticipated additional risks above what can be experienced during the scheduled surgery performed without the BAUM. If a complication occurs, [name] and/or the treating physician will review to determine if it is attributable to the use of the BAUM. Attribution determination will be made based on the type of complication and whether it is a medical or anesthetic complication of surgery, for example surgery complications may include bleeding or infection. Participants will be monitored for all complications for 25-35 days post surgery. If the standard-of-care post-operative visit is outside of the 25-35 day window, a clinician will call the patient during the 25-35 day window and document any post-operative complications.

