11.0 BIOSTATISTICS

The primary aim of the study is to show that the docking of the BAUM is feasible and subsequent uterine positioning is feasible. The BAUM will be considered successfully docked when the V-Care is inserted into the uterus and secured in place to the robotic arm to hold for the duration of the procedure. Interim data will be reviewed and presented.

We expect a very high percentage (90-95%) of patients to achieve successful docking and that the device will be held securely in place for the duration of the procedure. With 40 patients, the 95% confidence interval around a hypothetical 50% success rate is (35%, 65%); if the hypothetical success rate is 90% then the confidence interval is (81%, 99%), assuming binomial proportions. If the number of successes is less than 35 we will warrant re-design of the device and reassessment of its feasibility. The table below provides the probability of observing at least 35 successes (>=35) out of 40 patients under true hypothetical rates of success from 0.5 to 0. 9..

Obs	n	m	р	Prob of seeing >=35	Probability of seeing <35
1	40	35	0.5	0.00000	1.00000
2	40	35	0.6	0.00014	0.99986
				0.000.0	0.00400
3	40	35	0.7	0.00862	0.99138
4	40	35	0.8	0.16133	0.83867
5	40	35	0.9	0.79373	0.20627

Safety will be assessed by reporting all intraoperative complications during the surgery. Complications might include vaginal tear or uterine perforation. The number and type of complications will be reported. Among 554 patients who underwent laparoscopic or robotic-assisted hysterectomy at MSK from 7/1/14-6/30/15, there were 2 patients who experienced 2 true intraoperative complications. There are no expected postoperative complications, as the manipulator is removed following surgery so patients participating in the study will undergo routine follow-up. The study will stop for safety if we observe 2 intraoperative complications out of 40 patients. The table below provides the probability of observing at least 2 complications (>=2) out of 40 patients under true hypothetical rates ranging from 0.05 to 0.2. We expect the complication rate to be much smaller than 0.05.

Obs	n	m	р	Prob of seeing 2 or more	Probability of seeing 1 or less
1	40	2	0.05	0.60094	0.39906
2	40	2	0.10	0.91953	0.08047
3	40	2	0.15	0.98789	0.01211
4	40	2	0.20	0.99854	0.00146

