13.2 Data and Safety Monitoring

The Data and Safety Monitoring (DSM) Plans at Memorial Sloan Kettering Cancer Center were approved by the National Cancer Institute in September 2001. The plans address the new policies set forth by the NCI in the document entitled "Policy of the National Cancer Institute for Data and Safety Monitoring of Clinical Trials," which can be found at: http://cancertrials.nci.nih.gov/researchers/dsm/index.html. The DSM Plans at MSK were established and are monitored by the Office of Clinical Research. The MSK Data and Safety Monitoring Plans can be found on the MSK Intranet at: https://one.mskcc.org/sites/pub/clinresearch/Documents/MSKCC%20Data%20and%20Safety%20Monitoring%20Plans.pdf.

There are several different mechanisms by which clinical trials are monitored for data, safety, and quality. There are institutional processes in place for quality assurance (e.g., protocol monitoring, compliance and data verification audits, therapeutic response, and staff education on clinical research QA) and departmental procedures for quality control. In addition, there are two institutional committees that are responsible for monitoring the activities of our clinical trials programs: the *Data and Safety Monitoring Committee* (DSMC) for Phase I and Phase II clinical trials, and the *Data and Safety Monitoring Board*

(DSMB) for Phase III clinical trials. These committees report to the Center's Research Council and Institutional Review Board. This pilot trial will be reviewed by the DSMC.

Patients will be tracked for complications for 25-35 days post-surgery to record any postoperative complications that may be related to the robotic device. Any complications identified will be tracked in the study database. [name] and/or the treating physician will review to determine if it is attributable to the use of the BAUM. Once the first three patients complete their surgery and follow up, the IRB will be informed of how they have fared.

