14.2 Serious Adverse Event (SAE) Reporting

An adverse event is considered serious if it results in ANY of the following outcomes:

- Death
- A life-threatening adverse event
- An adverse event that results in inpatient hospitalization or prolongation of existing hospitalization
- A persistent or significant incapacity or substantial disruption of the ability to conduct normal life functions
- A congenital anomaly/birth defect
- Important Medical Events (IME) that may not result in death, be life threatening, or require hospitalization may be considered serious when, based upon medical judgment, they may jeopardize the patient or subject and may require medical or surgical intervention to prevent one of the outcomes listed in this definition

Note: Hospital admission for a planned procedure/disease treatment is not considered an SAE.

SAE reporting is required as soon as the participant signs consent. SAE reporting is required for 30-days after the participant's last investigational treatment or intervention. Any events that occur after the 30-day period and that are at least possibly related to protocol treatment must be reported.

If an SAE requires submission to the IRB office per IRB SOP RR-408 'Reporting of Serious Adverse Events', the SAE report must be sent to the IRB within 5 calendar days of the event. The IRB requires a Clinical Research Database (CRDB) SAE report be submitted electronically to the SAE Office as follows:

The report should contain the following information:

Fields populated from CRDB:

- Subject's initials
- Medical record number
- Disease/histology (if applicable)
- Protocol number and title

Data needing to be entered:

- The date the adverse event occurred
- The adverse event
- The grade of the event
- Relationship of the adverse event to the treatment (drug, device, or intervention)
- If the AE was expected
- The severity of the AE
- The intervention
- Detailed text that includes the following
 - A explanation of how the AE was handled
 - A description of the subject's condition
 - o Indication if the subject remains on the study
- If an amendment will need to be made to the protocol and/or consent form
- If the SAE is an Unanticipated Problem

The Pl's signature and the date it was signed are required on the completed report.

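### The one required postoperative contact may fall on days 25-29, before the 30-day SAE reporting period ends, and no later contact is required

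*Combined protocol and SAP*

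**What the plan says.** The follow-up period is given as 25-35 days in Sections 1.0, 4.2, 7.0 and 13.2. Section 4.2 states, in a sentence that ends by naming the device: "After surgery, patients will be followed by the study team for 25-35 days to record any postoperative complications that may be related to the robotic". Section 7.0 adds: "Participants will be monitored for all complications for 25-35 days post surgery". Section 13.2 repeats the window: "Patients will be tracked for complications for 25-35 days post-surgery to record any postoperative complications that may be related to the robotic device".

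Sections 4.2 and 7.0 also say how the follow-up is met. The standard-of-care visit serves if it falls in the window; otherwise, "If the standard-of-care post-operative visit is outside of the 25-35 day window, a clinician will call the patient during the 25-35 day window" and records any complications.

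The SAE period is set separately in Section 14.2: "SAE reporting is required for 30-days after the participant's last investigational treatment or intervention". Inside those 30 days there is no restriction to related events. Relatedness matters only afterwards: "Any events that occur after the 30-day period and that are at least possibly related to protocol treatment must be reported".

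Two other safety observations are mentioned. Section 4.2 has an early check: "Patients would also be assessed for complications immediately after surgery". Section 11.0 says that no postoperative complications are expected, "so patients participating in the study will undergo routine follow-up", and names no day for that follow-up.

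**The concern.** A contact can ask only about what has happened up to the day it takes place. If the last required contact comes before the reporting period ends, the protocol sets a reporting duty for days on which it plans no means of finding events. A site can follow the plan exactly and still finish a patient's follow-up with part of her SAE period open.

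The stake is the completeness of the late postoperative record for a prototype device in its clinical pilot. Section 4.1 says that an application for FDA approval may follow a successful trial. Section 13.2 adds a nearer use: the IRB is to be told how the first three patients did once their surgery and follow-up are complete. Under the present window that report could be written while one or more of those patients are still inside the 30-day period.

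**Working it through.** The plan gives no figure of its own to reproduce here. The check is day arithmetic on its stated windows.

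**Inputs**
- Permitted contact days: 25 to 35 after surgery (Sections 4.2 and 7.0), which is 35 - 25 + 1 = 11 days.
- SAE reporting period: 30 days after the last intervention (Section 14.2).
- Day of last intervention: the day of surgery, taken as day 0. The device is placed at the start of the case (Section 4.2), and the manipulator is removed after surgery (Section 11.0), so there is one exposure per patient.
- Target accrual: 40 patients (Sections 1.0 and 4.1).

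**Step 1. Days left uncovered.** For a contact on day *d*, the part of the SAE period still to come is max(0, 30 - *d*).

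| Contact day | Days of SAE period after contact |
|---|---|
| 25 | 5 (days 26-30) |
| 26 | 4 |
| 27 | 3 |
| 28 | 2 |
| 29 | 1 |
| 30 to 35 | 0 |

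The largest gap is 5 days, or 5/30 = 17% of the period.

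**Step 2. Share of the window that leaves a gap.** Days 25-29 are 5 of the 11 permitted days: 5/11 = 45%.

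**Step 3. Patients affected.** The documents do not say when standard visits or calls usually take place, so only a range follows.
- Every contact on day 30 or later: 0 of 40.
- Every contact on days 25-29: 40 of 40.
- Contacts spread evenly over the 11 days (an assumption): 40 × 5/11 = 18.2, about 18 of 40. The mean gap over all patients would be (5 + 4 + 3 + 2 + 1)/11 = 15/11 = 1.4 days.

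**Step 4. Does another required contact close the gap?** The check immediately after surgery is too early. The routine follow-up in Section 11.0 has no stated day. If the standard visit falls after day 35, the patient has a call in the window and then that later visit, but the visit belongs to routine care and is not a study requirement. No section requires a contact on or after day 30, or a second contact when the first falls on days 25-29.

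**Step 5. After the change.** With a day 30-35 window, max(0, 30 - *d*) = 0 for every permitted day.

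**The case against.** The strongest reply is that Section 14.2 sets a duty to report and does not set a visit schedule. It does not say that each patient must be questioned on the last day. The same duty begins at consent, and no dedicated contact is planned for that interval either. It also continues after day 30 for possibly related events, so no contact window could match it in full. Days 25-35 are day 30 plus or minus 5, an ordinary visit window. The follow-up is described as monitoring, which may mean more than a single contact, and the institutional SAE procedure and monitoring plans that the protocol refers to are not reproduced in it.

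Much of this stands, and it rules out several stronger readings:

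- A reader might infer that events on days 26-30 are never picked up. The text does not support that. The duty to report continues, and spontaneous reports, the medical record or a later routine visit may reveal an event. What is missing is a required contact that asks.
- A reader might infer that unequal follow-up, up to 35 - 25 = 10 days between patients, biases a planned rate. No section specifies a tabulation of postoperative complications. Section 11.0 reports the number and type of intraoperative ones.
- A reader might infer that the main safety conclusion is weakened. The safety outcome in Section 9.0 and the stopping rule in Section 11.0 both count intraoperative complications, so neither depends on this window.
- A reader might take 18 of 40 as an estimate. It rests wholly on the even-spread assumption, and it counts patients with a gap, not missed events.

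Two parts of the reply do not stand. A window centred on day 30 still allows contact on day 25, and monitoring for 25-35 days may still end on day 25. Neither reading covers days 26-30. The expectation of no postoperative complications does not settle the matter either, since it is what the follow-up would check.

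**Conclusion.** The point holds in a limited form. The follow-up window and the SAE period do not line up: a patient can complete the required follow-up on days 25-29 with 1 to 5 days of all-cause SAE reporting still open and no later required contact. The gap is possible for any patient and certain for none. Between 0 and 40 patients could be affected, and the documents do not allow a narrower statement.

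This rests on counting surgery as day 0, on a single exposure at surgery, and on reading the visit-or-call rule as the minimum that satisfies follow-up. The documents give no event rate for days 26-30, so the number of missed events cannot be estimated. The consequence is confined to the late postoperative complication and SAE record and the IRB report on the first three patients. It is worth correcting because the correction is cheap, not because any planned analysis or decision rule fails.

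**What to change.** Reconcile the follow-up window in Sections 1.0, 4.2, 7.0 and 13.2 with the SAE period in Section 14.2, so that the final required contact falls on or after day 30, for example day 30-35. Where the standard visit comes earlier, the clinician call already provided for is made on or after day 30 and asks about the whole period since surgery. State that postoperative complications are reported through a common day 30 for all patients, and that the IRB report on the first three patients is prepared once each has passed day 30.

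The cost is a short wording amendment, a contact window of 6 days in place of 11 (35 - 30 + 1 = 6), and additional calls to patients whose standard visit falls on days 25-29. The IRB report may come up to 5 days later. Sample size, the primary outcomes and the stopping rule do not change.
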